In a hospital in Barcelona, RPI was performed using the BioDent instrument on the tibia mid-shaft of 27 women (79.1 ± 7.8 years) recovering from an osteoporotic fracture and 8 controls with a similar age range (83.2 ± 5.3 years) (12). The indentation distance increase (IDI) for the fracture patients was 47% greater (i.e., more susceptible to damage formation) than for the non-fracture patients (p=0.008). In a follow-up study, the same research team performed similar RPI tests for 4 groups of patients: 20 with no history of a fracture

[figure not shown]

Fig. 1: The bone micro-anatomy gives rise 3 T_2 components when analyzed by ^1H NMR spectroscopy. One of these components, bound water correlates with the fracture toughness (K_{1c}) of bone.

or bisphosphonate (BP) use, 38 with typical hip fractures, 6 with atypical fractures (below lesser trochanter), and 6 on BP for 5 to 12 years (but no fracture). Total indentation distance (TID) and IDI were significantly higher (worse) for the fracture cases than for the non-fracture cases (no difference between typical and atypical). The proposed project aims to assess a new, hand-held RPI instrument (OsteoProbe) for its ability to discriminate osteoporotic bone from normal bone in comparison to the clinical gold standard DXA. Although the bone measurement from OsteoProbe at the tibia mid-shaft was found to be different between women with and without type 2 diabetes (13), there is currently no evidence that it is any better than DXA in predicting fracture risk.

Other New Assessment Tools for Fracture Resistance Assessment

Current efforts in the labs of the Co-PI [name] and his collaborators to improve fracture prediction include Raman spectroscopy (RS) (14-15), **(NMR) relaxometry** (i.e., quantitative, sub-voxel MRI) (16-17), and **reference point indentation (RPI)**. All these techniques can potentially be translated to the clinical assessment of bone, but NMR/MRI (18,19) and RPI (12,20) are closest to providing clinically useful information about bones. Moreover, the NMR technique can be combined with other MRI approaches that provide structural and architectural parameters of bone (21).

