After establishing the biophysical origins of proton signals within human cortical bone using NMR relaxometry (Fig. 1) (17), we reported that bound water can explain the age-related decrease in the material strength of human cortical bone ($r^2=62\%$, $p<0.001$) (22) and that loosely bound water detected by NMR contributes to bone toughness (16). Perhaps more relevant to diabetes and aging effects on bone, we found that bound water also correlates with the ability of bone to resist crack propagation (Fig. 1). We hypothesize that increasing pore water (intra-cortical porosity) and decreasing bound water (surrogate of 'matrix quality') makes bone susceptible to fracture.

BioDent-RPI is a relatively new analytical technique that provides properties related to the ability of tissue to resist micro-indentation (a micron-size probe tip penetrates bone tissue over 10-20 cycles in force control). As such, the best way to quantify resistance to indentation is still an unresolved issue, and differences in RPI properties are likely context or disease dependent. Thus, we performed a series of experiments to show that RPI i) is sensitive to bone tissue organization (anisotropy), ii) provides significant correlations, albeit weak, with apparent bone fracture toughness ($r^2=24\%$, $p<0.05$), and iii) resistance to indentation decreases with age (manuscript under review). We hypothesize that low resistance to indentation is indicative of fragile bone.

Innovation

The proposed studies are based on i) *novel view* that water, collagen, and damage are important to fracture resistance, ii) *state-of-the-art* analysis tools that go beyond bone mass to quantify properties of the matrix, and iii) *unique* access to patients with clear differences in fracture resistance through an orthopaedic clinical at VUMC that fixes 100 distal radius fractures per year. These studies have the potential to i) *shift the paradigm* of bone health to one that includes characteristics of the bone matrix and its contribution to microdamage resistance, and ii) *transform* the manner in which clinical diagnostic methods for bone health are developed, from solely X-ray based to include MRI-based and mechanical characterization tools.

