2.0 Rationale and Specific Aims

The goal of this study is to determine whether two new, non-X-ray techniques can discriminate between high-energy fractures of normal bone (trauma) and low-energy fractures (fragility) of osteoporotic bone. The current gold-standard for assessing fracture risk – areal bone mineral density (aBMD) by dual energy X-ray absorptiometry (DXA) – is not particularly effective at identifying individuals who are at risk of suffering a fracture (5, 23-25). Yet, there is a growing population of diabetics and elderly individuals prone to fractures (6, 26-28). In effect, the age-related and diabetes-related increase in fracture risk is independent of a person's aBMD (6, 7, 29, 30). These findings stress the urgency in developing diagnostic tools that can improve fracture risk prediction so that patients can be treated with the appropriate anti-fracture therapies.

Shifting from the current paradigm of using X-ray based modalities to assess fracture risk, the reference point indentation (RPI) method acquires direct measurements of 'material quality' of the bone tissue (31), while magnetic resonance imaging (MRI) assesses bound water and pore water concentrations that relate to the material properties of cortical bone (18,22). Specifically, the OsteoProbe-RPI engages the patient's bone, and upon applying an impact force, it measures the ability of the tissue to resist micro-indentation. Recently, this measurement – currently known as bone material strength (BMS) – was found to be lower in post-menopausal women with type 2 diabetes than age-matched women without diabetes (13). Our novel MRI methods utilize relaxation-selective preparations with ultra-short echo-time (UTE) acquisition to separately measuring bound and pore water concentrations on bone (19), which we postulate to reflect matrix quality and porosity (16). Despite the encouraging results from studies applying RPI and UTE-MRI to bone, there is no evidence that *a local measurement of bone material quality or bulk measurements of bound and pore water are predictive of fracture resistance at sites that are prone to fragility fractures.*

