By affirming the ability of these tools to discriminate a fragility (osteoporotic) fracture from high-energy (trauma) fracture, the proposed study will provide justification for large prospective studies that i) evaluate the ability of these techniques to predict fracture, ii) assess whether these techniques are informative on how drug therapy is affecting bone, and iii) whether intra-operative RPI is useful to surgical guidance (e.g., placement of bone screws).

AIM 1: DETERMINE WHETHER INDENTATION RESISTANCE IS DIFFERENT BETWEEN PATIENTS WITH FRAGILITY FRACTURES AND THOSE WITH HIGH ENERGY FRACTURES.

Hypothesis: Local indentation resistance (BMS) of the distal one-third radius is lower for patients with a fragility wrist fracture than healthy patients with a traumatic wrist fracture.

Approach: Men and women (>18 y.o.) undergoing surgery to fix a distal radius fracture involving the metaphysis will be recruited into the study. Exclusion criteria will include known risk factors of pathological fractures (e.g., bone metastasis) and long-term or recent treatment for osteoporosis (e.g., bisphosphonate). In addition to standard-of-care, the orthopaedic surgeon will indent the cortex between the one-third distal radius (10-15 sites separated by 2 mm) and the ultradistal (UD) site with the OsteoProbe prior to stabilizing the fracture with a volar plate. The patient's arm will be secured to prevent rotation of the bone. Postoperatively, the patient's hips, spine, and contra-lateral radius will be imaged by DXA to determine aBMD following standard protocols at the Vanderbilt Clinical Research

Center (CRC). Patients will be stratified into two groups: high-energy fracture (e.g., motor vehicle crash) of *normal bone* and low-energy fracture (e.g., fall from a chair or standing height) of *osteoporotic bone*. We expect BMS to be less for the fragility fractures than for non-osteoporotic fractures. In addition, the lower BMS for the fragility fracture group will be significant when including aBMD, age, and body mass index (BMI) as covariates.

AIM 2: DETERMINE WHETHER BOUND WATER AND PORE WATER ARE DIFFERENT BETWEEN PATIENTS WITH FRAGILITY FRACTURES THAN THOSE WITH HIGH ENERGY FRACTURES.

Hypothesis: Bulk bound and pore water of the distal one-third radius will be lower and higher, respectively, for patients with fragility wrist fractures than healthy patients with a traumatic wrist fracture.

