Approach: Postoperatively, patients in Aim 1 may also have their contralateral arm (distal one-third) imaged by our unique UTE-MRI technique (Philips Achieva 3T scanner) using wrist coil at the VUIIS. By including reference markers in the scan, the average concentration of bound water and pore water (mol ¹H per bone volume) will be quantified for a 14 mm axial segment (0.5 mm in-plane resolution). We will also image age-matched and gender-matched individuals without a history of fractures to the operative fracture patient group. We expect the fragility fracture patients to have significantly less bound water and more pore water than high-energy fracture patients and non-fracture patients, and this difference will be significant after adjusting for aBMD and BMI. In addition, bound water will be less and pore water more for the elderly fragility fracture group than for the elderly non-fracture group (also adjusting for aBMD). A group of non-operative distal radius fracture patients will also be recruited to undergo a DXA scan at the CRC and some of those patients will be asked to undergo an MRI scan at VUIIS.

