10.0 Statistical Considerations

Data will be analyzed using the statistical software package Stata (version 11.0, College Station, TX) with the assistance of [name], Biostatistician III. Statistical comparisons will be performed using two-sided tests at the 5% significance level. Mann-Whitney test will assess whether differences in properties between groups are statistically significant. Next, general linear models (GLMs) will be used to determine whether the case explains each property after adjusting for aBMD (or T-score), BMI, and age. Using a robust analysis with GLMs, the data will be bootstrap with 500 replicates. Based on the variance from our cadaver studies and expected mean BMS for 'normal' bone as measured by Farr et al. (32), a sample size of 15 per group will provide 87% power to detect a 11.2% difference between the 2 cases at an α of 0.05. With 60 participants (15 per variable) will allow us to determine whether fracture type significantly explains BMS after adjusting for 3 covariates (aBMD, BMI, age). Note that there will be overlap in the participants between Aim 1 and Aim 2. From our limited imaging studies, we can expect bound and pore water of normal bone to be 22 mol $^1\text{H}/\text{L}$ and 10 mol $^1\text{H}/\text{L}$. A sample size of 10 per group will provide 81% power to detect a 22.8% and 51.8% difference in bound and pore water at an α of 0.05. Note that these changes are typically associated with a significant decrease in bone strength by destructive testing (18, 22). With 20 per group we can include a covariate in the regression models.

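### Does the 15-per-variable ratio in Section 10 leave the adjusted BMS comparison without an adequate sample size?

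*Protocol*

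**What the plan says.** Protocol Section 10.0 gives one power statement for BMS: "a sample size of 15 per group will provide 87% power to detect a 11.2% difference between the 2 cases". The variance comes from cadaver work and is not stated as a number. The tests follow the general rule "Statistical comparisons will be performed using two-sided tests at the 5% significance level". The next sentence moves to the adjusted model: "With 60 participants (15 per variable) will allow us to determine whether fracture type significantly explains BMS after adjusting for 3 covariates". The model terms are fracture type, aBMD (or T-score), BMI and age. Section 5.0 sets enrolment at 30 high-energy and 30 low-energy operative fractures.

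Section 2.0 states the Aim 1 hypothesis as lower BMS in fragility than in traumatic wrist fractures, with no mention of covariates. Under the approach it adds the expectation that "the lower BMS for the fragility fracture group will be significant when including aBMD, age, and body mass index (BMI) as covariates". Section 1.0 describes the instrument as being assessed "for its ability to discriminate osteoporotic bone from normal bone in comparison to the clinical gold standard DXA".

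**The concern.** Read literally, Section 10.0 promises that 60 participants will settle the adjusted question and backs the promise with a rule of thumb. A subjects-per-variable ratio is 15 whether fracture type is unrelated to aBMD, BMI and age or nearly determined by them. The precision of the fracture-type coefficient depends heavily on that overlap. Its size depends on how much of the group difference the covariates absorb. The 87% figure does not help, because no covariate enters it.

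Some overlap is plausible here. Section 5.0 labels the groups as osteoporotic and otherwise normal bone, and aBMD is a covariate. For age, Section 2.0 mentions an elderly fragility fracture group, and Section 1.0 reports that indentation resistance falls with age, although with the older cyclic BioDent instrument.

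At stake is how a null adjusted result would be read. Whether BMS adds to aBMD is the question raised by the comparison with DXA. A reader who takes Section 10.0 at its word could treat a non-significant adjusted coefficient as evidence that BMS adds nothing.

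**Working it through.** **Inputs from the protocol.** Two-sided alpha 0.05; 15 per group, 87% power and an 11.2% difference (Section 10.0); 30 per group enrolled (Section 5.0); four model terms plus an intercept.

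**Assumed, because the protocol gives no figure.** R², the share of variation in fracture type explained jointly by aBMD, BMI and age; and k, the share of the 11.2% difference left after adjustment.

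**1. The ratio.** 60/(1 + 3) = 15. This is correct.

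**2. The plan's own power figure.** The SD is not stated, so 87% cannot be reproduced independently; the standardised difference it implies can be solved for. With the noncentral t, df = 28 and noncentrality d × √(15/2), 87% power gives d = 1.168. The implied SD is 11.2/1.168 = 9.59% of the mean. The figure is consistent with a plain two-group comparison.

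**3. Unadjusted power at the enrolled size.** Noncentrality = 1.168 × √(30/2) = 4.52, df = 58, power 99.4%.

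**4. Adjusted power at the enrolled size.** Noncentrality = d × k × √(15(1 − R²)/v), df = 60 − 5 = 55. Here v is the residual variance relative to the unadjusted within-group variance. With k = 1, v is kept at 1. If the covariates absorb a = d(1 − k), they must explain some within-group variance, so v can be at most 1 − a²(1 − R²)/(4R²). The table uses that bound, the least favourable value.

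| Share of 11.2% retained | R² 0.2 | 0.3 | 0.5 | 0.6 | 0.7 |
|---|---|---|---|---|---|
| all | 97.8% | 96.1% | 88.1% | 80.2% | 68.2% |
| four fifths | 90.5% | 85.6% | 71.6% | 61.7% | 49.7% |
| two thirds | 82.0% | 73.7% | 57.0% | 47.5% | 37.3% |

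Example, full difference at R² = 0.5: noncentrality = 1.168 × √(15 × 0.5) = 3.20, the same as in step 2. Doubling the group size exactly offsets a variance inflation of 1/(1 − 0.5) = 2.

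By this formula, 80% power holds up to R² of about 0.60, 0.39 and 0.22 in the three rows.

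**5. Check by simulation.** This used 20,000 runs per setting, with one informative and two noise covariates and R² taken as the population value. With the full difference, power is about 85 to 86% at R² = 0.5 and 77% at 0.6. With two thirds retained it is about 80, 71 and 55% at R² = 0.2, 0.3 and 0.5. These are 2 to 3 points below the formula because noise covariates raise the R² seen in the sample. The table values are therefore approximate and not lower limits.

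**6. What the R² values mean.** For one covariate and equal groups, the separation of group means is 2√(R²/(1 − R²)) SD: 1.0, 1.3, 2.0, 2.4 and 3.1 SD for R² of 0.2, 0.3, 0.5, 0.6 and 0.7. The right-hand columns need strongly separated groups.

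**The case for a change.** The strongest case for a change is that Section 10.0 makes an affirmative claim of sufficiency, so this is more than an omission. Across the table, the same 15 per variable goes with power from 98% to 37%, so the ratio cannot carry the claim. The adjusted result is also no side issue: Section 2.0 predicts that it will be significant, and it bears directly on whether BMS adds to DXA. Correcting the sentence would cost almost nothing.

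The logical part stands: the ratio is not power, and the 87% is unadjusted. The rest carries less weight. Section 10.0 names power where it means power (87% for BMS, 81% for bound and pore water) and names none for the adjusted model. For the imaging aim it follows the same pattern: a power statement for the basic comparison, then a larger group size so that a covariate can be fitted. The sentence on 60 participants fits that model-size reading, although its verb is too strong. The 98% to 37% span describes an assumed grid; its low end needs R² = 0.7 with a third of the effect absorbed. The supporting passages are also indirect. "bound water will be less and pore water more for the elderly fragility fracture group than for the elderly non-fracture group" is an imaging contrast under Aim 2, and the age result comes from a different instrument. The statement that the "age-related and diabetes-related increase in fracture risk is independent of" aBMD concerns fracture risk; it does not tell us how far these two groups differ in aBMD, in either direction.

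**Conclusion.** No change to the plan is needed. The sentence is loosely justified, but nothing in the protocol shows 60 to be too few, and no stated figure is wrong. On the implied SD of 9.59% of the mean, 30 per group gives about 99% power for the unadjusted Aim 1 hypothesis. For the adjusted coefficient it gives about 85 to 88% at R² = 0.5 if the full 11.2% survives. Adjusted power drops below 80% with R² near 0.6, or with weaker overlap if the covariates take up part of the difference. The adequacy of 60 for the adjusted question is therefore unsupported, not disproved.

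A fuller justification or an exploratory label would leave enrolment, measurements, model and estimate the same. The one practical risk, over-reading a null adjusted result, is met at reporting: give the adjusted coefficient with its confidence interval, and do not take non-significance as evidence that BMS adds nothing to aBMD. Sections 2.0 and 7.0 already present the study as groundwork for larger prospective studies, which limits the weight such a result would bear.

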11.0 Privacy/Confidentiality Issues

During this study every attempt will be made to keep the patient's protected health information (PHI) private. To reduce this risk, most study data will be maintained in the Vanderbilt REDCap database. Vanderbilt Redcap is a secure, web-based application for building and managing online databases. The data obtained and stored in Redcap will only be accessible by research personnel. All Redcap data will be de-identified prior to statistical analysis. All Osteoprobe measurements taken will be relayed from the Osteoprobe to a laptop (which is connected to the instrument during the surgical case). The imported data will be displayed in an excel spreadsheet. This excel spreadsheet will be saved on a key study personnel password-protected computer(s). In addition, some data from the excel spreadsheet will be transferred to the Redcap study database. Any physical study forms (ex. consent documents, screening forms, surveys) will be kept in a locked cabinet in the Vanderbilt Hand & Upper Extremity Center Administrative Offices for 6 years following completion of the study. Following this 6 year period, all physical study forms will be disposed of in shred-it confidentiality bins provided by VUMC, and all Osteoprobe data kept in Excel spreadsheets will be permanently deleted from the key study personnel computer(s).

12.0 Follow-up and Record Retention

The duration of this study will last until we have enrolled and completed follow-up on all 110 patients. All study records will be kept for six years following study closure, at which time the database/excel spreadsheets will be deleted and all forms will be disposed of properly.

